8.2.3. End of Treatment Safety Follow-up Visit

A Safety Follow-up visit should occur 30 days (± 7 days) from the last dose of study treatment or prior to the start of a new anticancer treatment. If the subject starts a new anticancer treatment less than 7 days after the treatment termination visit, only those procedures not conducted at the treatment termination visit should be performed at the Safety Follow-up visit.

Subjects who withdraw consent to treatment may still participate in Safety Follow-up. The following procedures will be performed at the Safety Follow-up visit:

- Complete physical exam including weight and eye-related symptom assessment
- Evaluation of ECOG performance status
- Vital signs
- Review of AEs and concomitant medications
- 12-lead ECG (in triplicate [≥ 1 minute apart])
- Collect blood samples and urine for the following clinical laboratory tests:
 - Hematology
 - Serum chemistry
 - Coagulation
 - Urine pregnancy test (for women of reproductive potential only)
 - Urinalysis

8.3. Follow-up Phase

Once a subject has completed the End of Treatment Safety Follow-up visit they will enter the Follow-up Phase. Subjects that discontinue treatment for reasons other than progressive disease and full withdrawal of consent will participate in ongoing response follow-up.

8.3.1. Response Follow-up

Subjects who discontinue the study for reasons other than PD through Cycle 37 will be followed every 16 weeks until the date that would have corresponded to the planned Cycle 37 and then every 24 weeks (± 7 days) from the last CT or MRI scan until PD, up to the end of the study. Subjects who discontinue the study for reasons other than PD after Cycle 37 will be followed every 24 weeks (± 7 days) from last CT or MRI scan until PD, up to the end of the study. During this period, scans and related response evaluation assessments will be carried out as follows: CT scan for target, non-target, and new lesion assessment, radiographic spleen and liver assessment, and overall disease assessment. In cases where the subject is being evaluated for CR, the following should also be performed: PET scan to confirm CR; bone marrow disease assessment to confirm CR; and MRD central lab upon CR.

8.3.2. Survival Follow-Up, Subsequent Anticancer Therapy Collection, and Long-term Surveillance of Other Malignancies

Once a subject progresses (for subjects who have not withdrawn consent for follow-up), he/she will be contacted approximately every 24 weeks (± 7 days) from the last dose by clinic visit or telephone to assess survival for up to the end of the study. Subsequent anticancer therapies, best response to therapy, and information about other malignancies will be collected. Subjects will be contacted until death, subject withdrawal, lost to follow-up, or study termination by the Sponsor, whichever occurs first.

8.3.3. Missed Evaluations

Missed evaluations should be rescheduled and performed as close to the original scheduled date as possible. An exception is made when rescheduling becomes, in the investigator's opinion, medically unnecessary or unsafe because it is too close in time to the next scheduled evaluation. In that case, the missed evaluation should be abandoned.

9. SUBJECT COMPLETION AND WITHDRAWAL

9.1. Completion

A subject will be considered to have completed the study if he or she has died before the end of the study, has not been lost to follow up, or has not withdrawn consent before the end of study.

9.2. Withdrawal from Study Treatment

Study treatment will be discontinued in the event of any of the following events:

- Progressive disease
- Unacceptable toxicity: an intercurrent illness or AE that prevents further administration of study treatment or completion of rituximab dosing during induction phase
- Withdrawal of consent for treatment by subject
- Investigator decision (such as chronic noncompliance, significant protocol deviation, or best interest of the subject)
- Study termination by Sponsor
- Subject becomes pregnant

All subjects, regardless of reason for discontinuation of study treatment will undergo an End of Treatment Visit and be followed for progression and/or survival.

The investigator should notify the Sponsor within 24 hours if a subject discontinues study treatment (ibrutinib/placebo and/or rituximab) due to disease progression and should provide documentation of disease progression for review by the Medical Monitor. If a subject shows signs of disease progression on physical examination or laboratory assessment, the subject

should continue study treatment until disease progression is confirmed by the investigator using the revised criteria for malignant lymphoma described by the International Working Group for NHL ([Cheson 2014](#)). These subjects should stay in the study to be followed for survival.

9.3. Withdrawal from Study

Withdrawal from study (including all follow-up) will occur under the following circumstances:

- Withdrawal of consent for follow-up observation by the subject
- Lost to follow-up
- Study termination by Sponsor
- Death

If a subject is lost to follow-up, every reasonable effort should be made by the study site personnel to contact the subject. The measures taken to follow up should be documented.

When a subject withdraws before completing the study, the following information should be documented in the source documents:

- Reason for withdrawal
- Whether the subject withdraws full consent (i.e., withdraws consent to treatment and all further contact) or partial consent (i.e., withdraws consent to treatment but agrees to participate in follow-up visits).

10. STATISTICAL METHODS AND ANALYSIS

Statistical analysis will be done by the Sponsor or under the authority of the Sponsor. A general description of the statistical methods to be used to analyze the efficacy and safety data is outlined below. Specific details will be provided in the Statistical Analysis Plan.

This study evaluates ibrutinib + rituximab (Arm A) vs. placebo + rituximab (Arm B) with 2 interim analyses and the primary analysis planned when the study observes 200 PFS events, or if pre-specified boundaries are crossed at an interim analysis. The final analysis for OS is planned when 165 OS events are observed or five years after enrollment of the last subject, whichever is earlier.

10.1. Subject Information

10.1.1. Intent-to-Treat (ITT) Population

The ITT population consists of all subjects randomized. The ITT population will be the primary population for all efficacy analyses. All the subjects will be analyzed according to the treatment arms to which they are randomized.

10.1.2. Safety Population

The Safety population consists of all subjects who received at least 1 dose of study treatment (rituximab, ibrutinib/placebo).

10.1.3. Pharmacokinetic Population

All subjects who received at least 1 dose of study treatment and had at least one post-treatment sample obtained.

10.2. Endpoints

10.2.1. Primary Endpoint

- Progression-free survival (PFS)

10.2.2. Secondary Endpoints

- Overall response rate (ORR) ([Cheson 2014](#))
- Overall survival (OS)
- Infusion-related reaction rate (Arm A vs. Arm B)
- Duration of response (DOR) as assessed by investigator
- Frequency, severity, seriousness, and relatedness of adverse events (AEs)

10.2.3. Exploratory Endpoints

- Health-related quality of life (QOL) as measured by the FACT-Lym
- Pharmacokinetic parameters or metrics of systemic exposure of ibrutinib and rituximab
- Evaluation and/or identification of relevant patient populations defined by biomarker(s)
- Minimal residual disease (MRD)-negative rate defined as the proportion of FL subjects who reach MRD-negative disease status
- Complete response rate at 30 months (CR30) as defined by the International Working Group (IWG) Revised Response Criteria for Malignant Lymphoma ([Cheson 2014](#))

10.3. Sample Size Determination

Sample Size Consideration for PFS

A sample size of approximately 440 subjects will be randomized to Arms A and B to evaluate whether Arm A will result in prolongation of progression-free survival (PFS) when compared to Arm B in treatment naïve subjects with follicular lymphoma. The sample size is determined according to the Group Sequential Design. For this calculation, the references used for the assumptions were [Hainsworth 2002](#), [Ghielmini 2004](#), [Zucca 2019](#), and [Fowler 2020](#). Assuming exponential survival distribution for the PFS events and 66.7% improvement in median PFS of Arm A over Arm B (a hazard ratio [HR] of 0.60), the study has ~ 87% power with 200 observed

PFS events using an overall 1-sided significance level of 0.025. For the sample size calculation, a median PFS of 28 months in the control arm, the actual enrollment rates using the 3-month average until November 2020, and a projected enrollment rate of 8 subjects per month afterwards were used. Two interim analyses are planned with the first interim analysis (IA1) for futility and the second interim analysis (IA2) for efficacy. The first interim analysis (IA1, futility) will be conducted when approximately 55% of the 200 PFS events have occurred. The futility boundary is based on a Rho parameter of 5. The second interim analysis (IA2) for efficacy is planned after approximately 75% of the 200 PFS events (ie, 150 PFS events) are observed and after the last subject has been enrolled, with approximately 90% of the subjects reaching at least 1 year of study follow-up. The efficacy boundary is based on the unequally weighted Bonferroni method allocating 1-sided alpha of 0.001 to IA2 and 0.024 to the primary analysis (PA) (Table 9).

Table 9. Futility and Efficacy Boundaries for Interim Analysis for PFS

Look #	Info. Fraction	Events	Cum. 1-sided α Spent	Boundary (1-sided p-value)	
				Efficacy	Futility
1	0.55	110	0	NA	0.5596
2	0.75	150	0.001	0.001	NA
3	1	200	0.025	0.024	0.024

Power Consideration for ORR

For ORR if we assume a response rate of 0.57 (Zucca 2019) in Arm B and a response rate of 0.73 (PCYC-1125-CA; Fowler 2020) in Arm A, then the power will be approximately 85% for a 1-sided alpha of 0.025 and sample size of 440.

Power Consideration for OS

The final analysis for OS is planned when 165 OS events are observed or five years after enrollment of the last subject, whichever is earlier. The study has ~80% power for the OS analysis at an overall 1-sided alpha of 0.025 when 165 OS events have occurred. An interim analysis for OS will be conducted at the time of the primary analysis of PFS when the superiority boundaries for PFS and ORR are crossed. It is anticipated that 140 and 165 OS events in total will be observed at the interim analysis (at ~77 months, corresponding to the timing of the PFS PA) and the final analysis (at ~91 months), respectively. This is based on the assumption that the 36-month OS landmark estimate is 73% for Arm B (Batlevi 2020) and 82.8% for Arm A (PCYC-1125-CA; Fowler 2020), i.e., a HR of 0.6 and control arm median OS of 79.29 months. The 1-sided alpha boundaries are 0.015 and 0.0207 at the interim analysis and final analysis, respectively, based on Lan-DeMets spending function with O'Brien-Fleming boundary ensuring control of overall type-1 error. In addition, a separate futility analysis without spending alpha is planned for OS at the second interim analysis, and details will be described in the SAP. The Sponsor may consider extending follow-up to attain more OS events to account for the impact of COVID-19.

The futility and efficacy interim analyses will be performed by the DMC. The Sponsor will remain blinded to the data and interim results if the study will continue. Exact alpha boundary will be calculated using the actual events observed at the interim analyses. Details will be included in the SAP.

10.4. Efficacy Analysis Methods for Primary and Secondary Endpoints

10.4.1. Analysis Study

10.4.1.1. Primary Endpoint PFS

Progression Free Survival, as assessed by the investigator, will be analyzed in the ITT population, comparing the 2 treatment arms (Arm A and Arm B) at an overall 1-sided 0.025 significance level using the log-rank test stratified by the randomization stratification factors: age group, FLIPI-1 score and ECOG performance status score. Distribution of PFS will be summarized for each treatment arm using the Kaplan-Meier (KM) method. The estimate of the hazard ratio between the two arms and its corresponding 95% CI will be computed using a Cox proportional hazards model stratified by the randomization stratification factors. In stratified efficacy analysis, small strata are combined to form bigger strata with ≥ 10 events and ≥ 40 patients in each stratum.

PFS is defined as duration from the date of randomization to the date of first documentation of disease progression or date of death due to any cause, whichever is first reported, prior to the use of subsequent anti-cancer therapy. Subjects who initiated subsequent anti-cancer therapy before disease progression or death will be censored at the last adequate disease assessment before the use of subsequent anti-cancer therapy. Subjects who are progression-free and alive, or have unknown status will be censored at the last adequate disease assessment. Subjects with no postbaseline disease assessment will be censored at randomization date. Adequate disease assessment is defined as having sufficient evidence to correctly indicate that progression has or has not occurred.

Supplementary/sensitivity analyses may be conducted using different censoring rules and will be described in the SAP.

10.4.1.2. Secondary Endpoints ORR and OS

If the primary endpoint comparison of PFS between Arms A and Arm B has demonstrated statistical significance, then secondary endpoints will be tested sequentially following a hierarchical order with ORR ranked first followed by OS.

ORR of the two treatment arms will be compared using the Cochran-Mantel-Haenszel (CMH) chi-square test, stratified by the randomization stratification factors, under the hierarchical procedure.

Overall survival is defined as the interval between the date of randomization and the date of the subject's death from any cause. If a subject is not known to have died (this includes subject with unknown death date), OS will be censored at the date the subject was last known to have been alive. Subjects who are known to be alive as of their last known status will be censored at their date of last contact. Subjects who are lost to follow-up will be censored at the date the subject is last known to have been alive. The last known alive date will be determined by selecting the last available date of any study procedures.

OS will be analyzed using the same method as for PFS.

The details of estimand framework, stratification factors used in the stratified analysis, and other statistical details will be specified in the SAP.

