# 1 INTRODUCTION

The statistical analysis plan (SAP) version 7.0 is based on the protocol amendment 4 dated February 07, 2023. This SAP defines key elements including variable definitions, and statistical methods for analysis of data in evaluation of efficacy and safety of PCYC-1141-CA. Analyses of biomarker and pharmacokinetics (PK) data are not in the scope of this document.

[figure not shown]
Throughout this SAP, "study treatment" and "study drug" are used interchangeably, and both are referring to ibrutinib, placebo, and/or rituximab.

Analysis methods specified in this document take precedence over those described in the protocol should there be any differences.

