ORR assessed by investigator	The proportion of subjects achieving a best overall response of CR or PR based on Cheson 2014 (Lugano Classification Criteria) per investigator assessment at or prior to initiation of subsequent anti-cancer therapy. Subjects who did not have any post-baseline disease assessments or initiated subsequent anti-cancer therapy prior to initial CR/PR will be considered non-responders when summarizing ORR.	
CMH chi-square test controlled for the pre-specified stratification factors, rate ratio and 95% CI.
 
Sensitivity Analysis:
 
ORR by IRC: same analysis as above.
 
A forest plot will be provided for subgroups.

DOR	DOR is defined as the time from initial CR or PR to PD or death due to any cause, whichever is first reported, regardless of discontinuation of study treatment. If such event does not occur, then subjects will be censored at the last adequate disease assessment as required for PFS censoring.	
Duration of response (DOR) by investigator: Kaplan-Meier estimates and associated CIs.
 
Censoring rules for DOR will follow the censoring rules as the PFS primary analysis for US and Other Regions, respectively.
 
Sensitivity Analyses:
 
Same as the PFS sensitivity censoring rules for US and Other Regions, respectively.
 
DOR by IRC: same analysis as above

OS	Time from the date of randomization to the date of death from any cause. Subjects who are not known to have died will be censored at the last known alive date.	
Efficacy analysis is similar to the PFS primary analysis. Unstratified log-rank test, unstratified Cox regression model to estimate HR and its associated CI will be applied if the stratification factors selected for the PFS primary analysis do not warrant stratified analysis. Kaplan-Meier estimates, median OS, and associated CI. A forest plot will be provided for subgroups.
 
Supplementary analysis:
 
 
• censor subjects who died due to COVID-19 at the day prior to the death date.
 

Endpoint	Definition	Analysis Method
Rate of infusion related reaction	Proportion of subjects experiencing infusion related reactions (IRR) that start on the day of a rituximab infusion and are assessed as related or possibly related to rituximab.	Chi-square test, rate ratio and 95% CI. For each treatment, Clopper-Pearson method is used for 95% CI of the estimated rate.

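### The protocol's OS rule censors a known death whose date is unknown, and the SAP neither clearly overrides it nor says how to date such a death

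*Protocol*

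**What the plan says.** Protocol 10.4.1.2 gives the OS definition: "Overall survival is defined as the interval between the date of randomization and the date of the subject's death from any cause". The next sentence sets the censoring rule for subjects not known to have died and widens that group in a parenthesis: "this includes subject with unknown death date), OS will be censored at the date the subject was last known to have been alive". The same paragraph says how the censoring date is found: "The last known alive date will be determined by selecting the last available date of any study procedures".

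SAP Section 1.2.2 also defines the OS estimand by death from any cause. The censoring rule in SAP Table 6 has no parenthesis: "Subjects who are not known to have died will be censored at the last known alive date". The SAP states its rank in Section 1: "Analysis methods specified in this document take precedence over those described in the protocol should there be any differences".

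The SAP has no convention for a partial or missing death date. Its only OS supplementary analysis concerns COVID-19 deaths. Section 8.1, which lists changes from the protocol's planned analyses, includes the interim OS boundary but nothing on OS censoring.

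**The concern.** A subject with an unknown death date is dead; only the date is missing. Classing that subject with those not known to have died contradicts the OS definition in the same section. The censoring is also informative, because it is applied on account of the death.

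OS is alpha-controlled, third in the testing order after PFS and ORR. Its event count triggers the final analysis, and its hazard ratio is compared with futility limits of 1.25 at the second PFS interim and 1.0 at the PFS primary analysis. A rule that removes known deaths affects each of these.

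The situation can arise. Under Protocol 8.3.2, survival contact after progression is about every 24 weeks and may be by telephone, so a site can learn of a death well after it happened. If telephone contacts are not treated as study procedures, the censoring date may also fall earlier than the last real contact.

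**Working it through.** **Which text governs an undated death**

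| Question | Protocol 10.4.1.2 | SAP |
|---|---|---|
| What is an OS event? | Death from any cause | Death from any cause |
| Who is censored? | Subjects not known to have died, expressly including those with an unknown death date | Subjects not known to have died; the category is not defined |
| What OS time does an undated death receive? | Time to the last known alive date, censored | Not stated |
| Is a change declared in SAP 8.1? | – | No |

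Read literally, the SAP would not censor a known death. But a death without a date has no OS time until a date is assigned, and the SAP assigns none. A programmer looking for an instruction finds only the protocol sentence.

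**Reproducing the plan's OS power**

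The inputs, from Protocol 10.3, are: "The study has ~80% power for the OS analysis at an overall 1-sided alpha of 0.025 when 165 OS events have occurred"; "a HR of 0.6 and control arm median OS of 79.29 months"; and "the 36-month OS landmark estimate is 73% for Arm B". Allocation is 3:1. The design values agree with each other under exponential survival:

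- Control median: 36 × ln 2 / (−ln 0.73) = 79.29 months.
- Hazard ratio: ln 0.828 / ln 0.73 = 0.600, using the protocol's 82.8% at 36 months for Arm A.

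Schoenfeld power is Φ(√(d × 0.75 × 0.25) × |ln HR| − 1.960). With d = 165 this is Φ(5.562 × 0.5108 − 1.960) = Φ(0.881) = 81.1%, which matches the stated figure of about 80%. At the SAP's final boundary of 0.024927 it is also 81.1%.

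**Effect of lost deaths on power**

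Let f be the share of deaths without a date. The documents give no value, so every f here is an assumption. Counted events are 165 × (1 − f), and true deaths needed for 165 counted events are 165 / (1 − f).

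| f | Deaths lost of 165 | Counted events | Power | True deaths needed for 165 counted |
|---|---|---|---|---|
| 0 | 0 | 165 | 81.1% | 165 |
| 1% | 1.7 | 163.4 | 80.7% | 167 |
| 2% | 3.3 | 161.7 | 80.3% | 168 |
| 5% | 8.2 | 156.8 | 79.1% | 174 |
| 10% | 16.5 | 148.5 | 76.9% | 183 |

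The power column applies only if the analysis is held at 165 true deaths. If undated deaths do not count toward the trigger and there is time to wait, the analysis reaches 165 counted deaths and power stays at 81.1%. The loss therefore needs the five-year cap to come first. Protocol 10.3 projects 165 deaths at about 91 months. With the 30-month accrual in Protocol 3.1, the cap falls at 30 + 60 = 90 months. The two triggers are thus close on the planning figures, but the actual accrual length is not given, so which comes first cannot be settled from the documents.

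**Effect on estimates**

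A simulation used 440 subjects, 3:1 allocation, uniform 30-month accrual, exponential survival with control median 79.29 months, a data cut at 165 true deaths, and lost deaths censored 0 to 24 weeks before death. It ran 3,000 trials per case with unstratified analyses.

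| True HR | Lost in Arm A | Lost in Arm B | Estimated HR | 36-month survival A / B |
|---|---|---|---|---|
| 0.60 | 0 | 0 | 0.601 | 82.8% / 73.0% |
| 0.60 | 5% | 5% | 0.604 | 83.6% / 74.2% |
| 0.60 | 5% | 0 | 0.568 | 83.6% / 73.0% |
| 0.60 | 0 | 5% | 0.635 | 82.8% / 74.3% |
| 1.0 | 5% | 0 | 0.951 | 74.2% / 73.0% |
| 1.0 | 0 | 5% | 1.061 | 73.0% / 74.3% |

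Equal loss leaves the hazard ratio alone and raises the 36-month estimates by about one point. One-sided loss shifts the hazard ratio. At a true HR of 1.0, 5% lost only in Arm A raises the one-sided type I error to about 0.05; 5% lost only in Arm B lowers it to about 0.015.

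**The case against.** The strongest reply is that the governing document does not contain the faulty rule. SAP Table 6 omits the parenthesis, and the precedence clause would then make a known death an event. This largely stands as a reading of Table 6, and it is why the protocol wording should not be presented as the settled OS rule. It does not close the matter: the SAP never says the category has been narrowed, does not declare a change, and supplies no date with which to analyse such a death.

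The reply on size also stands. A 24-week contact interval governs when a site learns of a death, not whether the date can be obtained, so undated deaths may be rare. The protocol parenthesis concerns an unknown date; nothing says that a partial date leads to censoring. The futility limits are non-binding, and the OS check at the second PFS interim has already been reviewed by the DMC.

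A reader might infer three stronger things that the documents do not support:

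- **That OS will be biased in favour of ibrutinib.** This needs more loss in Arm A. Both arms follow the same procedures, and investigators are blinded until the PFS primary analysis. If Arm B progresses earlier, as the design assumes, more of its subjects would be in telephone follow-up. Any excess loss would then fall there and move the hazard ratio toward 1.
- **That each lost death is counted as a survivor.** A censored subject leaves the risk set at the last known alive date. The fault is informative censoring, worth about one point at 36 months with 5% equal loss.
- **That PFS has the same fault.** The PFS rules in Protocol 10.4.1.1 carry no such parenthesis.

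**Conclusion.** The point holds as a defect of wording with a small expected effect. The protocol states a rule that contradicts the OS definition in both documents, and the SAP leaves two readings open for an alpha-controlled endpoint. With 1% to 5% of 165 deaths undated, about 2 to 8 events would be lost and power would be roughly 79% to 81%, still in line with the plan's figure of about 80%. That loss arises only if the five-year cap precedes 165 counted deaths. Bias in the hazard ratio is conditional on unequal loss between arms, for which the documents give no reason in either direction. The undated-death rates are assumptions throughout. The case for changing the text is that a decision on known deaths should not be left until after unblinding.

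**What to change.** Delete the parenthesis in Protocol 10.4.1.2, or override it expressly in SAP Table 6 and record that in SAP 8.1. In the SAP, state that:

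- every confirmed death is an OS event and counts toward the 165;
- a partial or missing death date is imputed between the day after the last known alive date and the date on which the death became known, using any partial date information;
- the number of imputed dates is reported by arm;
- a sensitivity analysis repeats OS under the censoring rule, or at the earliest and latest possible dates.

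The cost is a few lines of SAP text, an imputation step in the dataset specification, and a small error in the imputed dates. No new data collection or design change is needed beyond having the date the death became known available to programming. If no death is undated, the results do not change.
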